8.1.2 INCIDENCE RATES

Incidence rates will be calculated for all endpoints in all cohort groups; incidence rate ratios and 95% confidence intervals will be calculated as specified previously.

The incidence rate for all end points will be calculated using both the cumulative incidence approach and an incidence density (person-time) approach. The cumulative incidence approach will be used as the primary analysis and it will be calculated as in the following formula:

$$\text{Incidence rate} = (\text{Total new cases during follow-up period} / \text{Total persons at risk during follow-up period})$$

For this study, the numerator will be defined as the total number of patients with a diagnosis of primary end points or secondary end points during follow-up period. The denominator will be the total number of all patients at risk in cohorts groups during follow-up period.

Secondly, an incidence density approach calculates time at risk in person-years, measured from first prescription to the end of the observation period. The incidence rate will be reported as per 1,000 person-years of observation as shown in the following formula:

$$\text{Incidence Rate} = (\text{Total new cases during follow up period} / \text{Total person years during follow-up period}) * 1000$$

The numerator will be defined as the total number patients with end points of interest during follow-up period. The denominator will be defined as the sum of person years of patients during the follow up period. For patients who have incidence of primary or secondary end points, person time will equal the sum of days from their first prescription of treatment (index prescription) until the date of the incident condition (diagnosis of primary or secondary end points). For patients who do not experience an incidence of primary or secondary end points, person time will equal the sum of days from their first prescription of treatment (index prescription) to the last visit date or completion of 5 years follow up at which all patients will be censored, whichever occurs first.

In the determination of person years, the date of first prescription of treatment will be used as a surrogate for time of first exposure to treatment, since the date when the patient had their first treatment for osteoporosis may not be consistently ascertainable. The same definition of person-time ('ever' exposed approach accounting for all person-times of exposure) will be used for all the study endpoints given that they are all chronic diseases or malignancies with potentially long latency periods. If no primary end point occurs during the follow-up period, the duration will be calculated from the start of treatment date to the last patient visit or the end of study period, whichever comes first.

Both methods of calculating incidence rates will be used and the number of patients for whom the date of first treatment for osteoporosis could not be ascertained will be provided as part of the sensitivity analysis of the incidence density approach.

Stratifications by risks of interest (e.g. age, BMI, or selected medical history) will be performed for each outcome and descriptive summaries will be reported. For example, VTE incidence will be stratified according to age as well as by BMI. Other stratifications by medical co-morbidities and other variables of interest will also be performed as appropriate.

Given the rarity of certain malignancies in this population, the incidence rates observed in this study may be small and imprecise. To better characterize the rates obtained in this study, an additional analysis using external reference data for the malignancies will be conducted, i.e. a standardized incidence ratio (SIR). The observed frequency of malignancies in all three treatment groups will be compared with the expected frequency calculated from an age and gender matched population-based reference group (e.g., GloboCan). This SIR of observed versus expected events and 95% confidence interval, will be reported.

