4 HYPOTHESES AND DECISION RULES

4.1 STATISTICAL HYPOTHESES

Risk of the primary and secondary endpoints in each treatment cohort is equivalent:

- H_0 : Hazard_{bazedoxifene} = Hazard_{bisphosphonate} (Hazard Ratio [HR]=1)
- H_0 : Hazard_{bazedoxifene} = Hazard_{raloxifene} (HR=1)

That is, the null hypotheses will be that the rates of the primary endpoints events are the same in patients treated with BZA as in patients treated with bisphosphonate (or raloxifene). The null hypothesis for the analysis of each endpoint will be HR=1; the alternative hypothesis will be HR \neq 1.

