4.2 STATISTICAL DECISION RULES

Incidence rates of the primary and secondary endpoints will be calculated with a 95% Confidence interval (CI). The HR from Cox proportional hazard regression models will be used for comparison of event rates of the primary and secondary endpoints in each exposure (treatment) cohort. Statistical two-sided tests will be used with a significance level of 0.05.

Multiple Comparisons/ Multiplicity

No adjustments for multiple comparisons or multiplicity are planned among endpoints for this Post Authorization Safety Study.

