8.1.4 TIME TO EVENT ANALYSIS

A time to event analysis to compare the risk between treatment cohorts, i.e., the BZA, raloxifene and bisphosphonate treated groups, will be conducted for the primary end point (VTE) and other secondary endpoints if sufficient data are available,

[figure not shown]
The time to an event will be calculated as the time from index prescription date to the incidence date of primary end points. If a patient does not have a primary end point, the treatment duration will be based upon the index prescription date to the last visit or end of follow-up period, whichever comes first.

In order to ensure the exact duration from the start of treatment to the incidence of primary endpoints, a subgroup of newly prescribed patients who were diagnosed with osteoporosis during the enrolment period will be used first.

In the very unlikely event that the number of bisphosphonate or raloxifene patients are less than the number of BZA patients, the analysis will be extended to include bisphosphonate and raloxifene patients whose treatment began prior to the enrolment period. Considering the fact that bisphosphonates and raloxifene were launched before BZA (See the figure below), some patients could have already gotten treatment of bisphosphonates and raloxifene prior to the enrolment period (i.e., before BZA was launched). For such patients the start date will be the first date of treatment for bisphosphonates or raloxifene, available within the database.

Figure 1. Calculation of duration (from start date to the incidence of primary endpoint) for the treatment cohorts

The time to event analysis model will also be used to test for differences in time to event while adjusting for covariates of interest.

This model will take into account the duration to the incidence of the endpoint and control for imbalances in outcome risk factors, as determined based on the baseline descriptive analysis.

The following factors possibly related to the incidence of the primary end point will be considered.

- Treatment group (BZA, raloxifene, and bisphosphonate)
- Age
- BMI
- Reported history of smoking (If the reported frequency of smoking status is low this will be excluded)
- Reported Medical History of Diabetes, Hypertension, Malignancies
- Time since diagnosis of osteoporosis
- Previous treatment for osteoporosis (before index date) or Number of different treatments for osteoporosis in the entire patient history available
- History of DVT or PE

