8.2.2 INCIDENCE RATES

Incident rates of all primary and secondary endpoints for all three cohort groups (BZA/raloxifene/bisphosphonates) and 95% CI will be presented. The Hazard Ratio (HR) from Cox proportional hazard regression models will be used for comparison of event rates of the primary and secondary endpoints in BZA vs. bisphosphonate and BZA vs. raloxifene. A likelihood ratio test will test the null hypothesis of no difference in hazards in each pair-wise comparison. Statistical tests will use an alpha-level of 0.05.

The cumulative drug exposure of each treatment cohort will be categorized (1-30days/31-90 days/91-180 days) and used to evaluate whether or not the incidence rate of the primary and secondary end points varies with increased duration of treatment.

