8.2.4 TIME TO EVENT ANALYSIS

Time to event analysis will be conducted as a secondary analysis and the following factors possibly related to incidence of end points will be considered at the date of Incidence or the last visit before incidence: age, BMI, smoking (depending on availability of data), history of diabetes, history of hypertension, history of malignancies, history of VTE, and some other co-morbidities. Univariate Cox models (if applicable, depending on the PH assumptions for each factor, otherwise logistic regression model) will be performed for each factor and then, the analysis will be complemented by a multivariate Cox model (if applicable, depending on the PH assumptions for each factor) or a logistic regression. Hazard ratios (HR) or odds-ratios with 95% CI and p-values will be presented for significant factors at the 0.05 level.

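### The SAP labels cases divided by persons, which ignores follow-up time, the primary analysis, while its hypotheses and tests rest on a Cox hazard ratio that it elsewhere calls secondary

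*SAP*

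**What the plan says.** SAP 8.1.2 plans two incidence measures. Of the first it says: "The cumulative incidence approach will be used as the primary analysis". The formula is total new cases over total persons at risk. The second is introduced with "Secondly, an incidence density approach calculates time at risk in person-years" and is reported per 1,000 person-years. Both will be reported.

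The comparison between drugs is set elsewhere and on another scale:

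- SAP 4.1: "The null hypothesis for the analysis of each endpoint will be HR=1".
- SAP 4.2: "The HR from Cox proportional hazard regression models will be used for comparison of event rates of the primary and secondary endpoints", with two-sided tests at 0.05.
- SAP 8.2.2 repeats the Cox comparison for both pairs of drugs and adds: "A likelihood ratio test will test the null hypothesis of no difference in hazards in each pair-wise comparison".
- SAP 8.1.4 plans "A time to event analysis to compare the risk between treatment cohorts" and lists treatment group among the model factors.
- SAP 8.2.4: "Time to event analysis will be conducted as a secondary analysis". The models named there are Cox models, with logistic regression as the fallback.
- Protocol 7.2 makes a time-to-event analysis optional and secondary.
- SAP 8.2.5 lists the cumulative method as item i and the Cox method as item ii, and ranks neither.

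Protocol 7.1 sets the precision target as an incidence rate ratio built from rates per 1,000 patient-years. SAP 3 would extend the study to preserve that precision. Under SAP 2.1, follow-up without an event ends at the last visit or at 5 years, so it varies between women.

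**The concern.** There are two problems.

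The first is one of ranking. The analysis labelled primary has no hypothesis test attached, and the only planned test belongs to a method that another section labels secondary. A reader following 8.1.2 would headline the ratio of proportions; a reader following 4.2 would headline the hazard ratio. In a post-authorisation commitment on an identified risk, that choice should not be open once the results are known.

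The second is the measure itself. Cases divided by persons compares drugs fairly only if the cohorts are followed for similar lengths of time. A cohort that leaves the practices sooner has less time in which a VTE can be recorded, so its proportion falls even when its rate is unchanged. The measure is also not the rate ratio for which protocol 7.1 planned precision.

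**Working it through.** **Planning figure.** Protocol Table 3 (2,150 bazedoxifene, 8,600 bisphosphonate, true ratio 1) gives 0.6 to 1.7. The Wald interval is IRR × exp(±1.96 × √(1/d1 + 1/d0)), with d = n × mean years × 0.00174 (times the IRR for bazedoxifene).

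- With 15% loss each year, mean follow-up is 3.42 years, so d1 = 12.8, d0 = 51.2 and the interval is 0.54 to 1.84.
- With 15% taken once, mean follow-up is 5 × 0.85 = 4.25 years, so d1 = 15.9, d0 = 63.6 and the interval is 0.58 to 1.73. This variant matches 22 of the 24 limits in Table 3.

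How the 15% was applied is a separate matter. What counts here is that the target is a person-time rate ratio, not a ratio of proportions.

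**Inputs for the comparison.**

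- Bisphosphonate VTE rate r0 = 0.00174 per year (protocol 7.1); bazedoxifene rate r1 = true ratio × r0.
- Cohorts of n1 = 1,823 and n0 = 1,823 × 6 = 10,938 (SAP 5.4).
- Maximum follow-up 5 years.
- Annual loss of 15% (protocol 7.1), given overall and not by cohort. Every other loss rate below is assumed.

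**Formulas.** Hazards are constant, and annual loss p gives λ = −ln(1 − p).

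- Mean person-time m = (1 − exp(−5(r + λ))) / (r + λ)
- Proportion with an observed event = r × m

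**Bisphosphonate.** λ = −ln 0.85 = 0.1625 and m = 3.41 years. The proportion is 0.00174 × 3.41 = 0.00593, so 10,938 women give 64.9 expected cases.

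**Equal loss.** At 10%, 15%, 20% or 30% in both cohorts, the ratio of proportions is 1.00 when the truth is 1 and 1.99 when it is 2.

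**Unequal loss.** Bisphosphonate stays at 15% and bazedoxifene varies:

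| Bazedoxifene loss per year | Mean follow-up, true 1 (years) | Cases/persons ratio, true 1 | Cases/persons ratio, true 2 |
|---|---|---|---|
| 10% | 3.87 | 1.14 | 2.26 |
| 12% | 3.68 | 1.08 | 2.15 |
| 15% | 3.41 | 1.00 | 1.99 |
| 18% | 3.16 | 0.93 | 1.85 |
| 20% | 3.00 | 0.88 | 1.75 |
| 30% | 2.33 | 0.68 | 1.36 |

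At a true ratio of 1 the distortion is simply the ratio of mean follow-up, for example 3.00/3.41 = 0.88. The person-time ratio is 1.00 or 2.00 in every row. A 10% shift needs bazedoxifene loss of about 11% or 19%.

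**Confidence intervals.** These are log-scale Wald intervals, with SE² = 1/d1 + 1/d0 for the rate ratio and 1/d1 − 1/n1 + 1/d0 − 1/n0 for the ratio of proportions.

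| True ratio, bazedoxifene loss | Expected bazedoxifene cases | Cases/persons ratio (95% CI) | Rate ratio (95% CI) |
|---|---|---|---|
| 1.5, 10% | 18.4 | 1.70 (1.02 to 2.85) | 1.50 (0.89 to 2.52) |
| 2, 20% | 19.0 | 1.75 (1.05 to 2.92) | 2.00 (1.20 to 3.34) |
| 2, 30% | 14.7 | 1.36 (0.77 to 2.39) | 2.00 (1.14 to 3.52) |

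Across the 15 unequal-loss combinations (five loss rates by true ratios 1, 1.5 and 2), whether the interval excludes 1 differs between the measures in two: the first and third rows above. The first is marginal and the third uses an extreme loss rate. At a true ratio of 1, neither measure excludes 1 in any of them.

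**The case against.** The strongest reply is that the decision analysis is already settled. The SAP section on hypotheses and decision rules names the hazard ratio, and no test is attached to cases over persons. On this view, 8.1.2 ranks only two ways of describing incidence. Likewise 8.2.4, which goes on to say that "the following factors possibly related to incidence of end points will be considered", covers only risk-factor modelling. This is a reasonable guess at the intent, but no passage says so. SAP 8.1.2 uses the unqualified label of primary analysis and promises rate ratios in the same section. SAP 8.1.4 describes time-to-event analysis as comparing the cohorts, though not as the principal comparison and with a condition about sufficient data.

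Three further points stand and limit the weight of the concern:

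- SAP Table 1 closes enrolment in April 2014 and runs follow-up to April 2019, so every woman can reach 5 years. Unequal follow-up could come only from differing loss or timing of last visits, not from study closure.
- Both rates will be reported, so nothing is withheld and a reader could see them diverge.
- Making the hazard ratio primary moves away from protocol 7.2, which plans rate ratios and treats time-to-event as optional. The person-time rate ratio could be chosen instead, but SAP 4.1, 4.2 and 8.2.2 would then have to change.

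**Conclusion.** The concern holds and should be fixed. As written, the SAP gives the primary label to a measure without time in its denominator, puts every hypothesis and test on a hazard ratio, and calls the time-to-event method secondary. That conflict is certain from the text and does not depend on the calculations.

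The numerical consequence is conditional. It is negligible with equal loss. It is about 12% to 14% in the ratio if annual loss differs by 5 percentage points around 15%, and it can go in either direction. These figures assume constant hazards and loss unrelated to VTE risk. The documents do not show that follow-up differs between cohorts.

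Person-time and Cox analyses also need loss to be unrelated to VTE risk. Deaths, which SAP 2.1 says are not recorded in these databases, affect all the measures and are no reason to prefer one.

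**What to change.** 1. In SAP 8.1.2 and 8.2.5, make incidence density per 1,000 person-years, with its 95% CI, the primary incidence measure. Keep cases over persons as descriptive.
2. State once that the primary between-drug comparison for VTE is the Cox hazard ratio with the likelihood ratio test already set in 4.2 and 8.2.2. Report the crude person-time rate ratio as supportive and use it for the protocol 7.1 precision target.
3. In SAP 8.2.4, limit the secondary label to risk-factor modelling, and bring protocol 7.2 into line.

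It would also help, though it is a separate point, for the sentence in item 2 to say which planned version it means: univariate or multivariate, and cumulative-risk or as-treated.

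The cost is text changes in three SAP sections and one line of protocol 7.2, by amendment if this counts as a major modification under protocol section 7. No new data are needed, and every quantity is already planned.

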## **2.2. Endpoints**

The clinical endpoints for this study were determined based on the clinical and pre-clinical data from the bazedoxifene development program, class effects of other SERMs, and recommendations of the EU Rapporteurs.

Potential endpoints will be identified by an electronic search of the coded diagnosis fields of the medical records. The relevant diagnostic codes that will be used as operational definitions of each of the endpoints will be listed in the statistical analytic plan of the study. The available medical record of the identified cases for the primary endpoint will be retrieved and reviewed to confirm the diagnosis.

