## 6.3. Endpoint identification

The relevant diagnostic codes for each of the endpoints will be specified in the statistical analytic plan. Endpoints will be identified based on an electronic search for the relevant diagnostic codes in the diagnosis fields of the medical records during the follow up period.

For the identified potential cases, the electronic medical record will be retrieved and reviewed by a clinical expert to confirm the diagnosis for the following endpoints:

The primary endpoint:

- a. Venous thromboembolism (VTE) defined as deep vein thrombosis (DVT), pulmonary embolism (PE), retinal vein thrombosis, and sinus thrombosis.

Secondary endpoints

- b. Ischemic stroke
- c. Thrombotic and ischemic cardiac disorders (including myocardial infarction, myocardial ischemia, and coronary occlusion; and includes both acute and chronic disorders).
- d. Malignancies: Breast, ovarian, renal, thyroid and endometrial.
- e. Any ocular event with a vascular etiology (possibly indicative of retinal vein thrombosis, e.g. retinal arterial thrombosis, retinal hemorrhage, visual field defects of vascular origin).

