## **9. ADVERSE EVENT REPORTING AND SERIOUS ADVERSE EVENT REPORTING**

This study uses de-identified patient-level electronic health related databases (e-HRD), in which it is generally not possible to link (i.e. identify a potential association between) a particular product and medical event for any individual. Furthermore, while the identifiable patient criterion may be met, the identifiable reporter criterion will not. Thus, the minimum criteria for reporting an adverse event (i.e., identifiable patient, identifiable reporter, a suspect product, and event) are not available and adverse events are not reportable as individual AE reports.

However, this study protocol requires review of the patient medical chart and/or a narrative field in the dataset. If the reviewer identifies a SAE with explicit attribution to any Pfizer drug via patient chart and/or narrative review (and with an identifiable reporter), these SAEs should be reported to Pfizer or its representative for submission to regulatory authorities.

A serious adverse event (SAE) is defined as any untoward medical occurrence that at any dose:

- results in death;
- is life-threatening (i.e., at immediate risk of death due to the event);
- requires inpatient hospitalization or prolongation of existing hospitalization;
- results in persistent or significant disability/incapacity; or
- is a congenital anomaly/birth defect.

Medical and scientific judgment is exercised in determining whether an event is an important medical event. An important medical event may not be immediately life-threatening and/or result in death or hospitalization. However, if it is determined that the event may jeopardize

the patient or may require intervention to present one of the other outcomes listed in the definition above, the important medical event should be reported as serious.

Examples of such events are intensive treatment in an emergency room or at home for allergic bronchospasm, blood dyscrasias or convulsions that do not result in hospitalization, or development of drug dependency or drug abuse.

If there is a written notation in the medical chart/narrative field indicating that a physician attributed a serious adverse event to a Pfizer drug, Pfizer or its representative will complete an SAE form within 24 hours and submit it to Pfizer Safety. Such information will not include any patient or physician identifying information such as name, address, or phone number.

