6 ENDPOINTS AND COVARIATES

The following Primary end points and Secondary end points will be identified with appropriate diagnosis codes. The detailed list of diagnosis codes in each country is available in a separate document.

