Venous Thromboembolic Events (VTE) are defined as deep vein thrombosis, pulmonary embolism, retinal vein thrombosis, and venous sinus thrombosis. This objective is to compare this incidence in real life settings with validated diagnosis codes, ICD9 in Italy and International Classification of Primary Care (ICPC) codes in Spain.

The availability of medical history of all relevant medical diagnosis for patients will be checked in both the Spanish and the Italian database and presented if available. The variables of medical history (diabetes, hypertension, VTE and Malignancies) will be presented in classes (Yes/No) before index date. (All the detailed diagnosis codes of each endpoint have been validated by Pfizer and are available in a separate reference document). For all medical history and smoking status, if the relevant information is not found in the database, it will be assumed to be negative.

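### The SAP does not carry over the protocol's record-review confirmation of VTE: it defines cases by diagnosis codes and uses the review result in no analysis, which can bias the bazedoxifene ratio

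*SAP*

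**What the plan says.** The protocol sets two steps. Codes find potential endpoints, and then, for VTE, "The available medical record of the identified cases for the primary endpoint will be retrieved and reviewed to confirm the diagnosis" (Protocol 2.2). Protocol 6.3 gives the task to a clinical expert: "For the identified potential cases, the electronic medical record will be retrieved and reviewed by a clinical expert to confirm the diagnosis". Its list covers VTE, ischemic stroke, thrombotic and ischemic cardiac disorders, five named cancers and ocular events of vascular origin. Protocol 9 also relies on the step, stating that "this study protocol requires review of the patient medical chart and/or a narrative field in the dataset".

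The SAP describes only the first step. In section 6 the endpoints "will be identified with appropriate diagnosis codes". In 8.1.2, "The cumulative incidence approach will be used as the primary analysis", and its numerator is "the total number of patients with a diagnosis of primary end points or secondary end points during follow-up period". SAP 8.1.1 presents the VTE comparison as resting on validated codes and adds that "All the detailed diagnosis codes of each endpoint have been validated by Pfizer". The time-to-event analysis in 8.1.4 runs to the date of the endpoint, with no reference to confirmation. The sensitivity analyses listed in 8.2.5 concern the recent-exposure window and missing covariates.

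**The concern.** The two documents give different case definitions for the primary endpoint. Validating a code list is not the same as confirming an individual case, and neither document reports a PPV or specificity for the VTE codes. Even if the review is done before the analysis file is built, the SAP does not say whether a rejected case leaves the numerator, how a case is counted when the record is too thin to decide, or whether coded-only results are shown. Two programmers following the SAP could produce different primary results.

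The data source adds weight to this. Protocol 3.2 and 10 say that hospital information reaches the GP file unsystematically and without linkage, so a VTE code may stand for an event diagnosed elsewhere. VTE is a labelled risk of BZA (Protocol 1.1) and the purpose of the study is to quantify it. A biased ratio in either direction would defeat that purpose.

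**Working it through.** **Side by side**

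| Step | Protocol | SAP |
|---|---|---|
| Find candidates | By code (2.2, 6.3) | By code (6) |
| Confirm | Expert review of the available record (2.2, 6.3) | Not mentioned |
| Count in the primary analysis | Not specified further | Patients with a diagnosis (8.1.2) |
| Undecidable records | Not specified | Not specified |
| Coded versus confirmed comparison | Not specified | Not specified |

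**Inputs**

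- Comparator VTE rate r0 = 1.74 per 1000 patient-years (PY), up to 5 years of follow-up, 15% annual loss, Wald 95% intervals (Protocol 7.1).
- 1,823 BZA and 10,938 bisphosphonate women (SAP 5.4); two-sided 0.05 (SAP 4.2).
- Assumed, because the documents do not give them: the comparator PPV (PPV0) and g, the BZA-to-comparator ratio of false-positive rates.

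**Reproducing the plan's figure**

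The interval is IRR × exp(±1.96 × √(1/d1 + 1/d0)), with d = n × PY per woman × rate. Take the 1:6 row of Protocol Table 3 (1,750 and 10,500 women) at IRR 2, with 5 × 0.85 = 4.25 PY per woman:

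- d1 = 1,750 × 4.25 × 0.00348 = 25.9
- d0 = 10,500 × 4.25 × 0.00174 = 77.6
- interval 1.28 to 3.12, against the stated 1.3 to 3.1

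All six limits of that row reproduce, and 22 of the 24 limits in the table. Compounding the 15% loss each year gives about 3.42 PY and matches only 3 of 24. Both follow-up figures are therefore carried below. The choice does not affect the size of the bias.

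**Effect of false positives**

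With comparator false-positive rate f = r0 × (1 − PPV0)/PPV0:

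observed IRR = (IRR × r0 + g × f)/(r0 + f)

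If g = 1, this reduces to 1 + PPV0 × (IRR − 1). For an event this rare, the same algebra applies to good approximation to the ratio of cumulative incidences.

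Equal false-positive rates (g = 1), SAP cohort sizes; events and intervals are for true IRR 2 at 4.25 PY:

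| PPV0 (assumed) | Observed, true 2.0 | Observed, true 1.5 | Events, BZA / bisphosphonate | 95% CI | Power at 4.25 PY | Power at 3.42 PY |
|---|---|---|---|---|---|---|
| 100% | 2.00 | 1.50 | 27.0 / 80.9 | 1.29–3.09 | 0.876 | 0.799 |
| 90% | 1.90 | 1.45 | 28.5 / 89.9 | 1.25–2.90 | 0.847 | 0.764 |
| 70% | 1.70 | 1.35 | 32.7 / 115.6 | 1.15–2.51 | 0.764 | 0.672 |
| 50% | 1.50 | 1.25 | 40.4 / 161.8 | 1.06–2.12 | 0.635 | 0.544 |

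Other splits of the false positives:

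- Equal PPV in both cohorts (g = true IRR): 2.0 stays 2.0.
- True IRR 1 with g = 1: stays 1.0.
- Over-coding under BZA (g = 3, PPV0 70%, so f = 0.4286 × r0): true 2.0 becomes (2 + 1.286)/1.4286 = 2.3, and true 1.0 becomes (1 + 1.286)/1.4286 = 1.6.

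**Precision lost by counting only confirmed cases**

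At true IRR 2, PPV0 50% and 4.25 PY, the standard error of the log ratio is √(1/27.0 + 1/80.9) = 0.222 for confirmed cases and √(1/40.4 + 1/161.8) = 0.176 for coded cases. The ratio is 1.26, so the interval is about 26% wider on the log scale. The same calculation gives about 12% at PPV0 70% and 3% at 90%. These figures assume that review confirms every true case.

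**The case against.** A reader might infer that the SAP drops the review and counts every coded VTE. The documents do not go that far. The SAP never says the review is abandoned, finding candidates by code is also the protocol's first step, and a patient with a diagnosis could mean one with a confirmed diagnosis. Protocol 7 lets the SAP modify the analysis but requires an amendment for major changes, and neither document records one for this step. The review could therefore take place before the numerator is formed. The code definitions are in a separate document that is not available here. Nor does the protocol promise confirmation of every VTE, since it speaks of the available record.

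A reader might also infer that unconfirmed codes must pull the ratio towards no harm. That requires a true ratio other than 1 and near-equal false-positive rates. Because VTE is a labelled BZA risk, more suspected-VTE coding among BZA users is plausible and would push the ratio upwards. The direction is not established.

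The practical objections also stand. Under Protocol 10, physicians cannot be queried, so some true VTEs will be unconfirmable. Protocol 9 expects the record reviewer to pick up serious events attributed to a sponsor drug, which full masking to drug would obstruct.

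None of this closes the gap. The SAP affirmatively describes a code-based comparison in 8.1.1 and gives the review result no role in the numerator, the Cox model or the sensitivity analyses.

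**Conclusion.** The concern holds as a conflict over the primary case definition. The protocol requires confirmation, while the SAP defines cases by code and assigns the review result to no analysis. It does not hold as a claim that the SAP has cancelled the review, or that the BZA ratio is necessarily biased towards 1.

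The size is conditional. With equal false-positive rates and comparator PPV between 90% and 50%, a true 2.0 is seen as 1.9 to 1.5, and power at 4.25 PY falls from 0.876 to between 0.847 and 0.635. With equal PPV there is no bias. With three times the false-positive rate under BZA and comparator PPV 70%, a true 1.0 appears as 1.6. PPV and the split of false positives are assumptions throughout.

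**What to change.** - In SAP 6 and 8.1.2, and in the Cox analysis of 8.1.4, define the primary VTE event as a case confirmed by record review.
- Do the same for the Protocol 6.3 endpoints that are also SAP endpoints. Endometrial cancer is on the review list but is not a named SAP endpoint. Gastrointestinal and lung cancers are SAP endpoints that are not reviewed. The SAP should therefore state that the malignancy aggregate mixes confirmed and coded cases.
- State how cases with insufficient records are counted, for example excluded from the primary numerator and included in a sensitivity analysis.
- Report all coded cases as a sensitivity analysis, with the confirmed proportion by cohort. That proportion shows which bias pattern applies.
- Mask the reviewer to cohort where this is feasible without impeding the attribution review in Protocol 9. Neither document requires masking at present.
- If the sponsor instead intends code-only cases, a protocol amendment should say so, as Protocol 7 requires for major changes.

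The cost is mainly SAP wording, because the protocol already requires the review. Masking may need a second reader for the attribution task. Fewer events will be counted and intervals will widen by an amount that depends on the PPV, and further if review fails to confirm true cases.
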